4.1 INTERIM ANALYSES

The study will incorporate a group sequential design (GSD) in which an interim analysis will be performed to detect an 80% protective effect of the Tango Belt at 80% power. If a significant difference is found between the prospective Tango Belt subjects and historical controls at the interim analysis, the study will be stopped, and the Tango Belt deemed superior to SOC alone. If not, sample size reestimation will be completed, and enrollment will continue until a final sample size is reached to detect a 60% protective effect of the Tango Belt at 80% power and a 5% total level of significance.

Following the steps from section 4, we assumed subjects were followed for an average of 6 months, an annual fall-with-major-hip-injury rate of 15%, and sufficient historical control subjects to allow 1:2 allocation of subjects to treatment and control. This would require 134 subjects in the prospective Tango Belt group and 268 subjects in the historical control group at the interim analysis using the Pocock alpha-spending function as well as accounting for 30% attrition. At the end of the study (should the higher effectiveness target not be achieved at interim analysis), 268 total subjects would be required in the prospective Tango Belt group and 536 subjects would be in the historical control group.

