6.3 METHODS FOR WITHDRAWALS AND MISSING DATA

All practical monitoring and follow-up steps will be taken to ensure complete and accurate data collection. Since endpoints are assessed at the 180-day visit, it is anticipated that there will be approximately 30% attrition. Given the disproportionately high rate of death and other loss-to-follow up reasons within this population, multiple imputation approaches will be carried out for missing primary endpoint data on the ITT population. The primary effectiveness analysis will be performed on data that has the primary outcome multiply imputed.

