6.3.1 MULTIPLE IMPUTATION

Prior to propensity score matching, the intervention group may have missing information on the primary endpoint (i.e. major hip injury due to a fall), primarily due to premature withdrawal from the study.

At the time of the final analysis, if more than 20% of data is missing for the primary endpoint reported at the 180-day visit, then the primary endpoint will be multiply imputed and the analysis from section 7.2 will be repeated using both observed and multiply imputed data.

For the multiple imputation, a total of 50 imputed datasets will be calculated (Graham et al.). Fully conditional specification (FCS) logistic regression will be used to impute missing major hip injury due to a fall status (primary endpoint) using the baseline covariates of age, sex, ethnicity, race, mobility level (Independent, Limited Assist, Supervision, Extensive Assist, or Total Dependence), BIMS Score, and FES-I score.

The analysis for the primary endpoint will be carried out utilizing 50 datasets and then results will be combined using PROC MIANALYZE in SAS to obtain one overall test of significance.

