7.2 PRIMARY EFFECTIVENESS ANALYSIS

The primary effectiveness endpoint for this study is the proportion of subjects experiencing major hip injuries due to falls, as reported at the 180-day visit and will be presented for the Tango Belt and control groups using the ITT and adherence populations.

The proportion of subjects experiencing major hip injury due to falls is defined as the total number of subjects who experience a major hip injury due to a fall divided by the total number of subjects.

The primary effectiveness hypotheses are:

$$\begin{array}{l} H_0 \colon \pi_T \ \geq \ \pi_C \\ H_1 \colon \pi_T \ < \pi_C \end{array}$$

where π_T and π_C are the proportion of subjects experiencing major hip injuries due to falls in the Tango Belt and control group, respectively.

The null hypothesis (H_0) for this endpoint states that the true proportion of subjects using Tango Belt and experiencing major hip injuries due to falls is greater than or equal to the true proportion of subjects in the control group who experience major hip injuries due to falls. The alternative hypothesis (H_1) states that the true proportion of subjects using Tango Belt and experiencing major hip injuries due to falls is less than the true proportion of subjects in the control group who experience major hip injuries due to falls.

The proportion of major hip injuries by treatment group will be presented along with a 95% confidence interval using the Clopper-Pearson method. H_0 will be tested at a one-sided 0.025 level of significance using a logistic regression analysis to compare treatment groups while controlling for propensity score.

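### The SAP names no test statistic for the logistic model, and its only pooling rule is Wald-type with no provision for zero or very few belt events; this matters mainly at the interim.

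*Combined protocol and SAP*

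**What the plan says.** SAP 7.2 states that "H_0 will be tested at a one-sided 0.025 level of significance", "using a logistic regression analysis to compare treatment groups while controlling for propensity score". It does not say whether the p-value is Wald, likelihood-ratio, score or exact. SAP 7.3 uses the same model and level for hip fracture, ED visits and hospitalizations. The Clopper-Pearson intervals in both sections describe each arm separately and are not the test.

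On missing outcomes, SAP 6.3 says "The primary effectiveness analysis will be performed on data that has the primary outcome multiply imputed" and that "it is anticipated that there will be approximately 30% attrition". SAP 6.3.1 words imputation for the final analysis, with the condition "if more than 20% of data is missing for the primary endpoint reported at the 180-day visit". It then fits the analysis to 50 datasets, and "results will be combined using PROC MIANALYZE in SAS to obtain one overall test of significance".

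SAP 4.1 plans the interim for an 80% protective effect "using the Pocock alpha-spending function". If the interim is not significant, sample size is re-estimated and enrolment continues towards a 60% effect. No section of the protocol or SAP gives a rule for zero events, separation or non-convergence.

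**The concern.** The interim targets an effect so large that very few belt events are expected: 94 × 0.03 = 2.8 if the 6-month control risk is 15%, or 94 × 0.015 = 1.4 if it is 7.5%. With no belt events the maximum-likelihood log odds ratio is infinite and its standard error has no meaning. A test built on their ratio then cannot reject, however strong the data. With one or two events it can also be much weaker than a likelihood-ratio or score test of the same model.

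Pooling with PROC MIANALYZE uses exactly that estimate and standard error. Expected attrition of 30% exceeds the 20% trigger, so pooling is the expected route wherever 6.3.1 applies. The early stop, which is the purpose of the sequential design, could then be missed because of the test and not the data. Under SAP 6.5 the secondary endpoints also stay closed until the primary succeeds.

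**Working it through.** **Inputs.** Evaluable numbers 94 v 188 at the interim and 188 v 376 at the final (SAP 2 and 4). With the attrition allowance, 134 v 268 at the interim (SAP 4.1). Effects of 80% and 60% (SAP 4.1). Control risk: SAP 4 gives 15% as a proportion of subjects; SAP 4.1 gives 15% as an annual rate with 6 months of follow-up, about 7.5%. Both are carried through.

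**Interim level (computed, not stated in the SAP).** Pocock spending at half information: 0.025 × ln(1 + (e − 1) × 0.5) = 0.0155 one-sided, z = 2.157.

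**Reproducing the plan's 94.** Take p1 = 0.03, p2 = 0.15, ratio r = 2, difference d = 0.12, mean risk 0.11.
- n = [2.157 × √(3 × 0.11 × 0.89) + 0.842 × √(2 × 0.03 × 0.97 + 0.15 × 0.85)]² / (2 × 0.12²) = 81.5.
- Continuity correction: n/4 × [1 + √(1 + 2(r + 1)/(r n d))]² = 93.5, so 94, as stated.

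This match needs 15% to be the 6-month risk. At 7.5% the same formula gives 198.

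**Chance of zero belt events**, (1 − p1)^n:
- Interim, 80% effect: 0.97^94 = 5.7%; 0.985^94 = 24%.
- Final, 60% effect: 0.94^188 = 0.001%; 0.97^188 = 0.3%.
- Final, 80% effect: 0.97^188 = 0.3%; 0.985^188 = 5.8%.

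**Single tables, one-sided p, unadjusted.**

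| Belt | Control | Wald | Score |
|---|---|---|---|
| 0/94 | 14/188 | tends to 0.5 | 0.003 |
| 1/94 | 14/188 | 0.027 | 0.012 |
| 0/94 | 28/188 | tends to 0.5 | 0.00004 |
| 1/94 | 28/188 | 0.003 | 0.0002 |

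First row, score: (14/188) / √(0.0496 × 0.9504 × (1/94 + 1/188)) = 0.0745/0.0274 = 2.71. Last row, Wald: ln[(1/93)/(28/160)] = −2.79, SE = √(1 + 1/93 + 1/28 + 1/160) = 1.026, z = −2.72. Against 28/188, one to five belt events all reject by Wald (p 0.003 to 0.012) while zero does not, so a better result loses significance.

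**With a propensity covariate.** Newton fits with a simulated score at 0/94 v 14/188 behave the same way. As iterations go from 6 to 20, the belt coefficient runs from −4.7 to −18.7, its SE from 3.8 to over 4,000, and p from 0.11 to 0.50.

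**Power**, enumerating both binomials, complete data, unadjusted, one-sided 0.0155 throughout (the SAP states no final-look level):

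| Sizes | Effect | Control risk | Wald | Score |
|---|---|---|---|---|
| 94 v 188 | 80% | 15% | 0.80 | 0.89 |
| 94 v 188 | 80% | 7.5% | 0.09 | 0.47 |
| 134 v 268 | 80% | 15% | 0.95 | 0.98 |
| 134 v 268 | 80% | 7.5% | 0.42 | 0.71 |
| 188 v 376 | 60% | 15% | 0.86 | 0.87 |
| 188 v 376 | 60% | 7.5% | 0.45 | 0.50 |

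The Firth-penalised likelihood-ratio test gives 0.91 and 0.53 in the first two rows. At 94 v 188 the actual size is 0.011 to 0.014 for the score test and 0.013 to 0.014 for the penalised test, both below 0.0155.

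**Pooling 50 datasets by estimate and SE**, zero observed belt events, 30% missing, simulated at interim and final sizes. Imputing from belt data alone gives p of about 0.20 to 0.31. If controls also feed the imputation model, p is 0.16 to 0.34 at 7.5%. At 15% it is 0.008 to 0.018 at interim size and about 0.001 at final size, because imputed injuries enter the belt arm.

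**The case against.** The strongest objection is that the SAP never specifies Wald. A propensity-adjusted test of proportions, the SAP's own description, fits a score or likelihood-ratio test equally well, and such a test of the same model rejects easily at zero events. That stands: the fault is an unnamed statistic together with a Wald-type pooling rule, not a prescribed Wald test throughout.

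Second, 6.3.1 words imputation for the final analysis, while the zero-event risk lies mainly at the interim. This also stands in part. But 6.3 puts no such limit on its statement that the primary analysis uses imputed data, so pooling at the interim cannot be excluded.

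Third, a pooled interim would keep withdrawals and use up to 134 v 268, where the loss is smaller. That is right, and those rows are shown. They ignore the variance added by imputation.

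Fourth, the severe figures arise at 7.5%, where even the score test reaches only 0.47. The conflict between the annual and 6-month readings of 15% is a separate problem, and the main cause of low power there.

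A reader might infer that the best possible belt result would make the trial fail. The documents do not support that: SAP 4.1 and 4.1.1 send a missed interim to re-estimation and further enrolment. Nor do very few events always defeat Wald, since 1/94 v 28/188 rejects. That the imputation model cannot be fitted with no belt events is also an inference. It follows if the model uses belt subjects only, which the use of FES-I (listed in protocol 10.2 for intervention subjects) and the absence of control imputation (SAP 6.2.2) suggest but do not state.

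**Conclusion.** The point holds as a gap in specification with a real cost at the interim. Under the plan's own 80% effect, zero belt events has a 6% or 24% chance at 94 v 188, depending on how the 15% is read, and in that case a test from the estimate and standard error cannot reject. Overall interim power falls from 0.89 to 0.80 at 15% and from 0.47 to 0.09 at 7.5%. At the final look under the 60% effect, zero events has a chance of 0.3% or less and the choice of test matters little.

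These figures rest on an unadjusted, complete-data 2×2 comparison as a stand-in for the propensity-adjusted model, on half information at the interim, and on a level of 0.0155 that the SAP does not state. The change should be made before outcomes are compared, though it does not decide whether the trial can succeed.

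**What to change.** In SAP 7.2 and 7.3, for both looks, take the p-value from a test of the same propensity-adjusted model that is stable under separation: the Firth-penalised likelihood-ratio test, or the score test. Apply it one-sided by the sign of the estimated effect, and state that Wald p-values are not used.

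In SAP 6.3.1:
- Replace pooling of estimates and standard errors with a matching likelihood-ratio or score pooling rule, and check its size by simulation at 30% missingness. Pooled chi-square statistics carry no sign, so the direction rule must be written in. Wald-style use of Firth estimates is not enough: 0/94 v 14/188 gives p = 0.028, against 0.0015 for the penalised likelihood-ratio test.
- Use a penalised imputation model that can be fitted with no observed belt events, and say which subjects feed it.
- State whether imputation applies at the interim, so that 6.3 and 6.3.1 agree.

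The cost is SAP wording, some extra programming and a simulation; no additional subjects. The proposed pooling rule has not been tested here at 30% missingness, which is why the simulation is part of the change.

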7.3 Secondary Effectiveness Analysis

The secondary endpoints will also be tested using propensity score adjusted test of proportions with a hierarchical gate-keeping method to preserve the type I error rate (see section 6.5).

The secondary effectiveness endpoints for this study include the following:

- 1. The proportion of subjects experiencing fall-related hip fractures will be presented for the Tango Belt and control groups.
- 2. The proportion of subjects experiencing ED visits due to falls will be presented for the Tango Belt and control groups.
- 3. The proportion of subjects experiencing hospitalizations due to falls will be presented for the Tango Belt and control groups.

The secondary endpoints will be assessed using data reported at the 180-day visit using the ITT population.

The proportion of subjects experiencing a secondary event will be assessed separately following the methodology in section 6.5 and are defined as follows:

- 1. The proportion of subjects experiencing fall-related hip fractures is defined as the total number of subjects who experience fall-related hip fractures divided by the total number of subjects.
- 2. The proportion of subjects experiencing fall-related ED visits defined as the total number of subjects who experience fall-related ED visits divided by the total number of subjects.
- 3. The proportion of subjects experiencing fall-related hospitalizations defined as the total number of subjects who experience fall-related hospitalizations divided by the total number of subjects.

The secondary effectiveness hypotheses are:

$$H_0: \pi_T \geq \pi_C$$

 $H_1: \pi_T < \pi_C$

where π_T and π_C are the proportion of subjects experiencing a secondary event (i.e., hip fractures, ED visits & hospitalizations) due to falls is greater than or equal to the true proportion of subjects in the control group who experience a secondary event due to falls. The alternative hypothesis states that the true proportion of subjects using Tango Belt and experiencing a secondary event (i.e., hip fractures, ED visits & hospitalizations) due to falls is less than the true proportion of subjects in the control group who experience a secondary event due to falls.

The proportion of secondary events (i.e., hip fractures, ED visits & hospitalizations) by treatment group will be presented separately along with a 95% confidence interval using the Clopper-Pearson method. H_0 will be tested at a one-sided 0.025 level of significance using a logistic regression analysis to compare treatment groups while controlling for propensity score.

8 Adverse Events

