3.2.2 SECONDARY ENDPOINTS

The study's secondary endpoints include the proportion of each of the following:

- Hip fractures due to fall in the subjects receiving SOC as compared to subjects receiving SOC plus the Tango Belt.
- Emergency Department (ED) visits due to fall in the subjects receiving SOC as compared to subjects receiving SOC plus the Tango Belt.
- Hospitalizations due to fall in the subjects receiving SOC as compared to subjects receiving SOC plus the Tango Belt.

The secondary endpoints will be assessed using data reported between enrollment and the 180-day visit.

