6.2.2 HISTORICAL CONTROL POPULATION

Due to the retrospective nature of the control group, only observed data will be used in analyses. Control subjects missing information will not be used in the Propensity Score (PS) analysis as there will be no imputation of missing data for the HC population.

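### The SAP imputes only the primary endpoint and gives no rule for belt subjects who leave early in the three gatekept secondary analyses, so read literally their unobserved time counts as event-free

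*Combined protocol and SAP*

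**What the plan says.** **Scope of imputation.** SAP 6.3 states that "multiple imputation approaches will be carried out for missing primary endpoint data on the ITT population". SAP 6.3.1 imputes major hip injury status only, at the final analysis, "if more than 20% of data is missing for the primary endpoint reported at the 180-day visit". Neither section mentions hip fracture, ED visits or hospitalisations. On the size of the loss, SAP 6.3 says that "it is anticipated that there will be approximately 30% attrition", so the 20% trigger would be met in the planned scenario.

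**Secondary analysis.** SAP 7.3 says: "The secondary endpoints will be assessed using data reported at the 180-day visit using the ITT population". The ED endpoint is defined as "the total number of subjects who experience fall-related ED visits divided by the total number of subjects", and the other two secondaries are defined in the same way. The ITT set (SAP 5.2.1) requires run-in adherence only. Availability of endpoint data is a condition of the per-protocol set (SAP 5.2.2), not of ITT. The test is a logistic regression controlling for propensity score at one-sided 0.025, shown beside Clopper-Pearson intervals.

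**Event window.** SAP 3.2.2 is wider than SAP 7.3: "The secondary endpoints will be assessed using data reported between enrollment and the 180-day visit".

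**Controls.** SAP 6.2.2 says: "Due to the retrospective nature of the control group, only observed data will be used in analyses". Controls with missing information are excluded from the propensity score analysis and are not imputed.

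**Gate.** Under SAP 6.5 the secondaries are tested in the order hip fracture, ED visits, hospitalisations, and only after the primary endpoint has succeeded.

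**The concern.** The three secondary tests are part of the type I error strategy, so each can support a claim. With about 30% of belt subjects expected to leave, the result depends on what their missing follow-up is taken to be, and the SAP does not say.

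Two analyses fit the text. In the first, every ITT subject stays in the denominator and a leaver without a recorded event counts as event-free. That lowers the belt proportion even if the belt does nothing, while controls with missing information may be removed. In the second, the logistic model silently drops subjects with a missing outcome. The test then uses different subjects from those behind the proportions and intervals printed beside it, and from those behind the imputed primary. Because the SAP does not choose, the choice could be made after the data are seen.

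**Working it through.** **The plan's own figures.** Dividing the evaluable sizes by 0.70 gives 188 / 0.70 = 268.6 belt subjects (SAP: 268) and 376 / 0.70 = 537.1 controls (SAP: 536). These agree to within rounding.

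**Inputs**
- Belt group: 268 (SAP 4.1).
- Controls: 376 (before the attrition allowance) or 536 (with it), both from SAP 2. Which number would be usable is an assumption.
- Attrition: 30% (SAP 6.3).
- Control risk over the window: the documents give none for the secondaries, so 7.5%, 15% and 30% are assumed. A fall-related hip fracture falls within the protocol's definition of major hip injury (protocol 2.2), so its risk should not exceed that of the primary endpoint. SAP 4.1 calls the primary rate 15% annual with six months of follow-up: 15% × 6/12 = 7.5%. The value of 30% illustrates ED visits or hospitalisations.
- True effect: none.

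**Share of belt events captured.** If leavers exit evenly over the window, each contributes half of it on average. With events before exit counted, f = 0.70 + 0.30 × 0.5 = 0.85. The apparent relative reduction with no belt effect is 1 − 0.85 = 15%.

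**Error of one test.** With control risk r, belt risk p = f × r and m controls, the pooled z-test rejects with probability

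Φ[ ((r − p) − 1.96 × s0) / s1 ],

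where s0 = √( q(1 − q)(1/268 + 1/m) ), q is the pooled risk, and s1 = √( p(1 − p)/268 + r(1 − r)/m ).

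Worked case, r = 0.15 and m = 376:
- p = 0.85 × 0.15 = 0.1275
- q = (268 × 0.1275 + 376 × 0.15) / 644 = 0.1406
- s0 = 0.02779, s1 = 0.02746
- (0.0225 − 1.96 × 0.02779) / 0.02746 = −1.164, so the probability is 0.122

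| Assumed control risk | Belt risk shown | 376 controls | 536 controls | Nominal |
|---|---|---|---|---|
| 7.5% | 6.4% | 0.077 | 0.079 | 0.025 |
| 15% | 12.75% | 0.122 | 0.130 | 0.025 |
| 30% | 25.5% | 0.237 | 0.261 | 0.025 |

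Simulation of the same test agrees to within 0.004.

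**Smaller loss of events.** If only a quarter of leavers' events go unseen, f = 1 − 0.30 × 0.25 = 0.925. The error is then about 0.045 at 7.5%, 0.06 at 15% and 0.09 to 0.10 at 30%.

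**Alternative reading.** If the model drops missing outcomes and missingness is unrelated to outcome, 188 against 376 gives 0.022 to 0.025 for risks of 5% to 30%, so there is no inflation.

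These are rates for a single unadjusted test. Matching, propensity adjustment and correlation with the earlier tests in the hierarchy are not modelled.

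**The case against.** A reader might infer that the SAP orders leavers to be counted as event-free and so builds in a false benefit. No section says so. The primary endpoint has the same form of denominator, "the total number of subjects who experience a major hip injury due to a fall divided by the total number of subjects", and there missing outcomes are treated as missing. The phrase alone is therefore not a non-event rule, and a standard logistic regression would drop missing outcomes. This stands: the inflation is conditional on the literal reading.

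A reader might also take the reference in SAP 7.3 to data reported at the 180-day visit to mean that nothing from a leaver counts. Only 70% of belt events would then be captured, and with 376 controls the error would be 0.26 at 10% risk and 0.73 at 30%. The documents do not support this. SAP 3.2.2 opens the window at enrollment, protocol 5.4 records data captured before removal, and protocol 7.3 collects falls, ED visits and admissions at 90 days and at unscheduled visits.

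Four further points stand in whole or in part:
- **Gatekeeping.** The rates matter only once the earlier tests have succeeded. They are not overall false-claim rates. The gate can still open on a real hip effect while ED visits or hospitalisations are unaffected.
- **Death.** SAP 6.3 names death as a main cause of loss. No fall follows death, so that part of a leaver's time is correctly event-free and the bias is smaller.
- **Controls.** SAP 6.2.2 does not say whether missing information covers outcomes or only covariates. If incomplete controls stay in, the asymmetry shrinks. If those removed had more events, the exclusion works against the belt.
- **Coherence.** A reader might see a contradiction in a subject imputed with a major hip injury but counted as fracture-free. Protocol 2.2 defines major hip injury more broadly than fracture, so that combination is possible.

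**Conclusion.** The concern holds as a missing rule with material consequences, not as a proven bias. The SAP imputes one of four hypothesis-tested endpoints, places the other three in a population that includes subjects without outcome data, and does not say what happens to those subjects.

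Under the literal reading, with the exit pattern, sample sizes and control risks assumed above, error for one secondary test is roughly three to ten times nominal. For hip fracture, the first in the order, 0.08 to 0.13 is the relevant part of the range. Under the complete-case reading there is no inflation if missingness is unrelated to outcome, but the tests, the displayed proportions and the imputed primary then rest on different subjects. Size depends on how many leavers died, and direction is uncertain if excluded controls had more events. The change should be made, because either reading leaves a defect and the remedy is cheap.

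**What to change.** In SAP 6.3.1 and 7.3:
- Handle hip fracture, ED visits and hospitalisations with the same multiple imputation as the primary endpoint, in the same imputed datasets. Sections 6.3 and 6.3.1 must first agree on whether imputation is unconditional or depends on the 20% trigger, since the secondaries would inherit that rule.
- Keep every event observed before exit, and align the window in 7.3 with that in 3.2.2.
- Let an imputed or observed fall-related hip fracture imply major hip injury, but not the reverse.
- State one rule for incomplete follow-up and one for death, apply both rules to belt subjects and controls, and say in 6.2.2 whether missing information includes outcomes.
- Use the same subjects for the proportions, the intervals and the tests.

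The cost is SAP wording and modest programming. Secondary results may become less favourable to the belt.
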